9.1.7 Multiple Comparison/Multiplicity

This is a descriptive study, designed to characterize the growth rate of AAA and the progression of disease. Thus, this section is not applicable.

9.1.8 Confidence Interval

All confidence intervals will be 95% CIs.

9.2 Disposition of Subjects

Summary of Subject Disposition	
Population	: All subjects screened
Contents	: 
• All subjects screened• All screen failure subjects (include subjects who were enrolled but not randomized)
➢ Primary reason for screen failure• All subjects randomized
➢ Randomized to IQOS/CIG or enrolled in SC➢ Completed subject➢ Discontinued subject• Reason of discontinuation
Remarks	: Percentage will be presented. Percentage of screen failure will be calculated using the number of all screened subjects in the denominator. For disposition events after randomization, the denominator will be the number of subjects randomized to IQOS/CIG groups or enrolled in SC.
Output	Summary of Subject Disposition (Study Termination) -All Subjects Screened- Listing of Screen Failed Subjects and Reason Listing of Subject Disposition (Study Termination)

Confidentiality Statement

Data and information contained in this document are considered to constitute trade secrets and confidential commercial information, and the legal protections provided to such trade secrets and confidential information are hereby claimed under the provisions of applicable law. No part of this document may be publicly disclosed without the written consent of Philip Morris Products S.A

Summary of Protocol Deviations		
Population	:	All subjects screened
Contents	:	The number and percentage of both major and minor protocol deviations by category will be summarized.
Output		Summary of Protocol Deviation -All Subjects Screened- Listing of Protocol Deviation

Summary of Analysis Sets and Reasons for Exclusions from Analyses		
Population	:	All subjects screened
Group	:	
• Study Arm• Product Use Category
Contents	:	The number and percentage of subjects (included/not included/ reasons for not included) of analysis set defined in “Analysis Sets” will be presented.
Remarks	:	
• Denominator will be the number of subjects enrolled into each arm for the table displaying enrollement arms.• Denominator will be the number of subjects in each product use category for the table displaying product use categories.
Output	:	Summary of Analysis Sets and Reasons for Exclusions from Analyses -All Subjects Screened- Summary of Analysis Sets and Reasons for Exclusions from Analyses by Product Use Category -All Subjects Screened- Listing of Analysis Sets

9.3 Demographic and Other Baseline Characteristics

Summary of Demographics and Other Baseline Characteristics		
Population	:	FAS and Safety Set
Group	:	
• Study Arm• Product Use Category (for FAS only)

Confidentiality Statement

Data and information contained in this document are considered to constitute trade secrets and confidential commercial information, and the legal protections provided to such trade secrets and confidential information are hereby claimed under the provisions of applicable law. No part of this document may be publicly disclosed without the written consent of Philip Morris Products S.A

Contents	Refer to Descriptive statistics
Analysis variables	
 • Age [years] • Age ($50 \leq <75, 75 \geq$) • Sex (Male, Female) • Race (Asian, Black or African American, White, Native Hawaiian or Other Pacific Islander, American Indian or Alaska Native) • Nationality (Japanese, Non-Japanese) • Baseline Waist Circumference [cm] • Baseline Waist Circumference ($<50, 50 \leq <60, 60 \leq <70, 70 \leq <80, 80 \leq <90, 90 \geq$) • Baseline Weight [kg] • Baseline Height [cm] • BMI [kg/m^2] • BMI ($<18.5, 18.5 \leq <25, 25 \leq <30, 30 \leq <35, 35 \geq$) • Recent (within 1 year) History of Alcohol Addiction? • Recent (within 1 year) History of Substance Addiction? • Smoking Status • Maximum minor-axis diameter (mm) • Maximum minor-axis diameter (mm) 
 ➢ Male ($<40 \text{ mm}, \geq=40 \text{ mm}$) ➢ Female ($<35 \text{ mm}, \geq=35 \text{ mm}$)
Definition	
 • Use the value of age from SDTM datasets. • For the race, subjects can have multiple races. The percentages may not sum to 100.
Outputs	
 Summary of Demographics and Other Baseline Characteristics -FAS- Summary of Demographics and Other Baseline Characteristics -Safety Set- Summary of Demographics and Other Baseline Characteristics by Product Use Category -FAS- Listing of Demographics

Confidentiality Statement

Data and information contained in this document are considered to constitute trade secrets and confidential commercial information, and the legal protections provided to such trade secrets and confidential information are hereby claimed under the provisions of applicable law. No part of this document may be publicly disclosed without the written consent of Philip Morris Products S.A.

Summary of Smoking History	
Population	: FAS and Safety Set
Group	: 
• Study Arm• Product Use Category (for FAS only)
Contents	Refer to Descriptive statistics
Analysis variables	: 
• Have you smoked for at least the past 5 years prior to AAA diagnosis?• How many cigarettes per day have you smoked over the past 5 years prior to AAA diagnosis? [cig/day]• Have you been smoking in the last 12 months?• How many cigarettes per day have you smoked over the last 12 months? [cig/day]• Have you quit smoking within 2 months after AAA diagnosis?• Are you still abstinent now? 
Those questions below are only answered by those enrolled in a protocol version equal or after 6.
 
• Have you been using any heat-not-burn tobacco product(s), for example IQOS or GLO, in the last 12 months?• How many tobacco HeatSticks / tobacco sticks per day have you used over the last 12 months?• Have you been using any tobacco vapor product(s), for example PLOOM Tech, in the last 12 months?• How many tobacco capsules per day have you used over the last 12 months?• Have you completely quit smoking cigarettes or completely stopped using any other tobacco or nicotine-containing products 6 months ago or even longer?• Are you still abstinent now?
Output	: Summary of Smoking History -FAS- Summary of Smoking History -Safety Set- Summary of Smoking History by Product Use Category -FAS- Listing of Smoking History

Confidentiality Statement

Data and information contained in this document are considered to constitute trade secrets and confidential commercial information, and the legal protections provided to such trade secrets and confidential information are hereby claimed under the provisions of applicable law. No part of this document may be publicly disclosed without the written consent of Philip Morris Products S.A

9.4 Measurement of Product Adherence

Summary of Product Use	
Population	: FAS and Safety Set
Group	: 
• Study Arm• Product Use Category (for FAS only)
Contents	: Refer to Descriptive statistics
Analysis variables	: 
• For cigarettes
➢ Days of exposure to cigarettes [days]➢ Daily product consumption (cigarettes)[/day]• For IQOS
➢ Days of exposure to IQOS [days]➢ Daily product consumption (IQOS) [heatsticks/day]• For heat-not-burn other than IQOS
➢ Days of exposure to heat-not-burn other than IQOS [days]➢ Daily product consumption (heat-not-burn other than IQOS) [/day]• For e-cigarettes
➢ Days of exposure to e-cigarettes [days]➢ Daily product consumption(e-cigarettes) [/day]• For smokeless tobacco pipe
➢ Days of exposure to smokeless tobacco pipe [days]➢ Daily product consumption smokeless tobacco pipe [/day]• For smokeless tobacco product
➢ Days of exposure to smokeless tobacco pipe [days]➢ Daily product consumption smokeless tobacco pipe [/day]• For cigar/ pipe/ kiseru/ shisha
➢ Days of exposure to cigar/ pipe/ kiseru/ shisha [days]➢ Daily product consumption (cigar/ pipe/ kiseru/ shisha) [/day]• For nicotine replacement therapy
➢ Days of exposure to nicotine replacement therapy [days]➢ Daily product consumption (nicotine replacement therapy) [/day]

Confidentiality Statement

Data and information contained in this document are considered to constitute trade secrets and confidential commercial information, and the legal protections provided to such trade secrets and confidential information are hereby claimed under the provisions of applicable law. No part of this document may be publicly disclosed without the written consent of Philip Morris Products S.A.

Summary of Product Use	
Target visit	V3 to V8 Overall for the summary table and listing.
Output	Summary of Product Use -FAS- Summary of Product Use -Safety Set- Summary of Product Use by Product Use Category -FAS- Listing of Product Use Listing of Product Use Categories

9.5 Planned Statistical Analyses

9.5.1 Primary Analyses

9.5.1.1 Mean Growth Rates

Summary of the Annualized Mean Growth Rates in Patients Diagnosed with AAA		
Population	:	FAS
Group	:	
• Study arm• Product Use Category
Contents	:	
The primary endpoint is the comparison of the annualized mean growth rates of AAA diameter between patients who were randomized to IQOS use and patients who continue to smoke CIG. The growth rate is calculated as the slope of the linear regression fit to the maximum minor-axis AAA diameter values over the time by randomization arm.
 
Descriptive statistics for the annualized mean growth rates of AAA will be presented.

Target visit	:	V3 to V8
Sample code	:	Linear regression

$$\text{Study Day} = \text{Measured date of visit} - \text{measured date of Baseline} + 1$$

Confidentiality Statement

Data and information contained in this document are considered to constitute trade secrets and confidential commercial information, and the legal protections provided to such trade secrets and confidential information are hereby claimed under the provisions of applicable law. No part of this document may be publicly disclosed without the written consent of Philip Morris Products S.A.

Summary of the Annualized Mean Growth Rates in Patients Diagnosed with AAA

	<pre>proc reg data = TargDs outest=outds ; by subject; model AAA diameter = Study day ; ods output ParameterEstimates = out1; run ;</pre>
Output	
Summary of the Annualized Mean Growth Rates in Patients Diagnosed with AAA -FAS-
 
Summary of the Annualized Mean Growth Rates in Patients Diagnosed with AAA by Product Use Category -FAS-
 
Figure of the Annualized Mean Growth Rates in Patients Diagnosed with AAA -FAS-
 
Figure of the Annualized Mean Growth Rates in Patients Diagnosed with AAA by Product Use Category -FAS-
 
Listing of Maximum minor-axis AAA Diameter Growth
 
Listing of Statistical Output (REG procedure)
 
Listing of Statistical Output (REG procedure) by Product Use Category

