2.2 Purpose of the Study

The data available in the literature for AAA growth rates in Japanese patients who continue to smoke CC and patients who had stopped smoking are scarce. In consequence, a well-informed estimate of the expected effect size in the different study groups as well as an evaluation of the operational feasibility, in particular the IQOS study group, is difficult.

Therefore, the purpose of this study is to evaluate the reduction of the AAA annual growth rate in patients who switch from smoking CC to using IQOS as compared to patients who continue to smoke CC. The study also aims to provide context to the scale of reduction in the growth rate, by comparing the AAA annual growth rates for continuing to smoke and switching to IQOS with the AAA annual growth rate in smokers who had stopped smoking.

The data derived from this study will help to close the existing gaps in the literature and inform on the appropriate design for further research studies in this field.

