12.6 Primary Analysis

The primary analysis will be a descriptive analysis of patients who were randomized to IQOS use as compared to patients who were randomized to continue to smoke CC (IQOS arm versus CC arm) in the Full Analysis Set of AAA patients.

The primary endpoint is the comparison of the annualized mean growth rates in patients diagnosed with AAA between patients who were randomized to IQOS use and patients who continue to smoke CC. The growth rate is calculated as the slope of the linear regression fit to the maximum minor-axis AAA diameter values over the time by randomization arm.

Descriptive statistics for maximum minor-axis AAA diameter will be summarized at each visit and overall (across all patients). The primary endpoint will also be summarized by strata (maximum-minor-axis AAA diameter, CC consumption, sex).

Study evaluation criterion:

This is a descriptive study, designed to gain an understanding on the effect of complete switching from cigarettes to IQOS use compared to continued CC smoking on the AAA growth rate and disease progression. Dual use of IQOS on top of CC will be also investigated. There are no formal statistical hypotheses to be tested.

Evaluation Criteria:

No formal evaluation criterion is applied since this is a descriptive study.

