3 STUDY OBJECTIVES AND ENDPOINTS

3.1 Primary Objectives and Endpoints

The primary objective of this study is:

To evaluate the reduction in the AAA annual growth rate in patients who switch from smoking cigarettes (CIG) to using IQOS, as compared to patients who continue to smoke CIG (IQOS arm versus cigarette arm), also as compared to patients who had stopped smoking (IQOS arm

Confidentiality Statement

Data and information contained in this document are considered to constitute trade secrets and confidential commercial information, and the legal protections provided to such trade secrets and confidential information are hereby claimed under the provisions of applicable law. No part of this document may be publicly disclosed without the written consent of Philip Morris Products S.A

versus Smoking Cessation (SC) arm), and to evaluate the reduction in the AAA annual growth rate in patients who continue to smoke CIG as compared to patients who had stopped smoking (CIG arm versus SC arm).

Endpoints (to be assessed using all available diameter measurements from V3 to V8):

- Measurement of the maximum minor-axis AAA diameter in mm
- AAA annual growth rate (calculated by annualizing the slope of the linear regression over the available diameter measurements)

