4.3.1.2 SC Arm

Patients who had stopped smoking will be enrolled in the SC arm at Baseline Visit (V2) through the Interactive Web and Voice Response System (IXRS) without being randomized.

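### The primary endpoint is defined as a comparison of growth rates between arms, but the SAP plans only within-arm summaries and no between-arm difference with a confidence interval

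*SAP*

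**What the plan says.** Protocol 12.6 states: "The primary endpoint is the comparison of the annualized mean growth rates in patients diagnosed with AAA", between patients randomized to IQOS and patients who continue to smoke. SAP 9.5.1.1 repeats this. The primary objective in SAP 3.1 is wider. It covers IQOS against cigarettes, IQOS against cessation, and growth "in patients who continue to smoke CIG as compared to patients who had stopped smoking (CIG arm versus SC arm").

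SAP 9.5.1.1 gives the result to be produced: "Descriptive statistics for the annualized mean growth rates of AAA will be presented". SAP 9.1.3 defines that content for continuous data as n, missing, mean, SD, median, quartiles, range and a 95% CI, tabulated by group. The outputs listed in 9.5.1.1 are summaries, figures and listings by study arm and by product use category. None is a difference.

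On how the growth rate is obtained, the text calls it the "slope of the linear regression fit to the maximum minor-axis AAA diameter values over the time by randomization arm". The sample code in the same table runs the regression "by subject; model AAA diameter = Study day", which gives one slope per patient in mm per day.

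Protocol 2.2 says why the study is done. Data are scarce, so "a well-informed estimate of the expected effect size in the different study groups" is difficult, and the results should "inform on the appropriate design for further research studies in this field".

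**The concern.** An endpoint worded as a comparison should yield an estimate of the thing compared, with its precision. Here the plan stops one step short. It gives a mean and an interval for each arm and leaves the reader to form the three differences that the objective names.

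Readers who work from separate per-arm intervals tend to go wrong in one of two ways. They may judge by whether the intervals overlap, which is too strict, or take one arm's interval as the precision of the difference, which is too lenient. In a study meant to guide the design of later ones, the difference and its interval are what a reader will look for first.

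The mismatch between text and code is secondary. A definition should be reproducible from its words alone, and the day-to-year conversion and the smallest number of scans that gives a slope are both unstated.

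**Working it through.** The plan gives no figure to reproduce: it has no effect size, SD or power, and the target of 114 has no derivation. The check has two parts.

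**1. Passages side by side**

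| Item | Place | Content |
|---|---|---|
| Endpoint | SAP 9.5.1.1, protocol 12.6 | a comparison, IQOS and CIG |
| Objective | SAP 3.1, protocol 3.1 | three between-arm contrasts |
| Planned result | SAP 9.5.1.1 with 9.1.3 | within-group statistics and within-group 95% CI |
| Secondary biomarkers | SAP 9.5.2.2 | ratio of geometric LS means with 95% CI, against CIG |
| Hypotheses | SAP 3.5.1 | no confirmatory test |

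The biomarker row shows that the SAP regards a between-arm estimate with an interval as compatible with having no hypothesis to test. SAP section 7 does not explain why the primary endpoint is treated differently.

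**2. Size of the interval that would be reported**

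From the documents: scans every six months from V3 to V8, so t = 0.5, 1.0, ..., 3.0 years; 32 patients enrolled when recruitment was reviewed (protocol 4.4), with 15 more forecast as potentially eligible.

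Assumed, because the documents do not give them: 32/3, or about 11 per arm, with 16 from (32 + 15)/3 as a high case and 8 as a low case; SD of true growth rates 1-2 mm/year; scan error SD 1-3 mm.

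- Spread of visit times: Sxx = sum of (t - 1.75)^2 = 4.375.
- SD of a fitted per-patient slope: sqrt(slope SD^2 + scan SD^2 / 4.375).
 - Low case: sqrt(1 + 1/4.375) = 1.11 mm/year.
 - High case: sqrt(4 + 9/4.375) = 2.46 mm/year.
- 95% half-width for a difference, n per arm, equal SDs and complete data: t(2n-2) x SD x sqrt(2/n).
 - n = 11, low: 2.086 x 1.108 x 0.426 = 0.99.
 - n = 11, high: 2.086 x 2.461 x 0.426 = 2.19.

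| n per arm | Complete data (mm/year) | With exits, simulated (mm/year) |
|---|---|---|
| 8 | 1.19-2.64 | 1.19-2.79 |
| 11 | 0.99-2.19 | 0.98-2.56 |
| 16 | 0.80-1.78 | 0.80-1.91 |

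The simulated column uses unequal-variance t intervals. Patients leave at their first reading of 55 mm or more, baselines are uniform over 30-49 mm, and true arm means are 2.4 and 2.0 mm/year. All of these are assumptions. Every value is at least twice the 0.4 mm/year in protocol 2.1. That figure compares smokers with former smokers and is used only as a yardstick, not as an expected IQOS effect.

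**Why per-arm intervals are a poor substitute.** At n = 11 the per-arm half-width is t(10) x SD / sqrt(11) = 2.228 x SD / 3.317 = 0.67 SD. The half-width for the difference is 2.086 x SD x 0.426 = 0.89 SD. Requiring two intervals not to overlap demands a gap of 2 x 0.67 = 1.34 SD, about 1.5 times too strict. Taking one arm's interval as the precision of the difference understates it by about a quarter (0.67/0.89 = 0.75).

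**Minimum number of scans.** One scan gives no slope. With two scans six months apart, Sxx = 0.125 and the standard error is scan SD / sqrt(0.125) = 2.83 x scan SD, against 0.48 x scan SD with all six. SAP 8.1 admits a patient to the FAS on one valid non-safety assessment, so FAS membership does not guarantee a slope.

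**The case against.** The best defence is that the study is descriptive by design. Protocol 12.6 says so and sets no evaluation criterion. Per-arm n, mean and SD will be reported, and the unequal-variance interval follows from them exactly: difference +/- t x sqrt(s1^2/n1 + s2^2/n2). No information is lost, and per-arm means and SDs are what a later sample-size calculation needs. The table shells are a separate document not available here and may show a difference.

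Much of this stands. It makes the point a gap in planned reporting, not lost data or a wrong analysis. It does not explain why the primary endpoint has no between-arm estimate when the biomarkers do, and a difference with a CI tests nothing. SAP section 1 makes the SAP the place for methodology, so the estimate belongs there whatever the shells contain.

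Three stronger readings are tempting, and the documents do not support them.

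- **The SC arm is left out.** SC patients are "enrolled in the SC arm at Baseline Visit (V2) through the Interactive Web and Voice Response System (IXRS) without being randomized", so the phrase about randomization arm taken alone would miss them. But the Group row in 9.5.1.1 says study arm, and SAP 8.1 lists SC among the arms for analysis. SC growth rates are planned.
- **The outputs hold no effect-size information.** They hold the means and SDs from which it can be computed.
- **The wording would bias the result.** One pooled line per arm could understate a difference if patients with large aneurysms leave early. The by-subject code and the Group row make that reading unlikely, and its size depends on the assumed baseline: a true 0.40 becomes about 0.27-0.31 for a uniform 30-49 mm baseline, but 0.32-0.40 for narrower or smaller ones. At 11 per arm sampling error is larger than this.

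**Conclusion.** The point holds as a modest, worthwhile correction. The primary endpoint is called a comparison and the objective names three contrasts, yet only within-arm summaries are planned. This rests on the text of SAP 3.1, 9.1.3, 9.5.1.1 and 9.5.2.2 and needs no assumption, apart from the unseen table shells.

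The size of the resulting interval does rest on assumptions about arm sizes, slope SD, scan error and exits. Within the ranges shown, the half-width is roughly 1.0-2.6 mm/year at 11 per arm, so the sample cannot resolve a difference near 0.4 mm/year. This does not show that the planned analysis is invalid or biased. The mismatch between text and code is a clarification only: per-patient slopes are almost certainly intended.

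**What to change.** In SAP 9.5.1.1:

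1. Add the IQOS-CIG, IQOS-SC and CIG-SC differences in mean annualized per-patient slope, each with a 95% CI (unequal-variance t). Present them as descriptive estimates without p-values and label the two SC contrasts non-randomised.
2. Replace the phrase on randomization arm with wording to this effect: a regression line is fitted for each patient over the available V3-V8 measurements, and the slopes are summarised by study arm and product use category.
3. State the day-to-year factor. SAP 9.5.2.1.2 uses 365.25, while the annual adverse-event table in 9.5.4.1 uses 365-day years; the choice changes a slope by less than 0.1% but should be written down.
4. State that a patient needs at least two V3-V8 scans to have a slope, and report how many FAS patients have none.

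Record the change in SAP section 7 as an addition to, and clarification of, protocol 12.6.

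The cost is a few sentences and lines of code, with no new data. SAP section 1 requires amendments before database lock; if lock has passed, it provides for additional analyses to be described in the study report. The one downside is presentational: the intervals will be wide and will show how little this sample can say about a difference of the size cited in the protocol.

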5.2.1 Discontinuation from the study

Patients must be discontinued from the study for any of the following reasons:

- Withdrawal of informed consent.
- Discontinuation is considered to be in the interest of the patient from a safety perspective as judged by the Investigator.
- Positive or unclear pregnancy test.
- The Sponsor or Investigator terminates the study or the study terminates at a particular investigational site. If the Sponsor or the Investigator decides to prematurely terminate the study, the patient will be promptly informed. The investigational site/head of the medical institution should report the fact and the reason in writing to the IRB / IEC.
- Patient has to undergo open surgical AAA treatment or AAA endovascular repair (as per the treating physician's decision based on the standard of care as documented in the Guidelines for Diagnosis and Treatment of Aortic Aneurysm and Aortic Dissection¹).
- The patient experiences a rupture of his/her AAA.
- Patient becomes an employee of the investigational site, a tobacco company or any other parties involved in the study.
- Lost to follow-up.

Patients may be discontinued from the study for the following reasons:

- Non-compliance to the study procedures based on the judgment of the Investigator.

If a violation of selection criteria is detected after enrollment, patients might be discontinued from the study based on a case-by-case decision of the Investigator.

Confidentiality Statement

Data and information contained in this document are considered to constitute trade secrets and confidential commercial information, and the legal protections provided to such trade secrets and confidential information are hereby claimed under the applicable provisions of applicable law. No part of this document may be publicly disclosed without the written consent of Philip Morris Products S.A.

Patients will not be discontinued from the study for the use of tobacco or nicotine-containing products other than their assigned product/regimen unless judged by Investigator.

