8.1 Full Analysis Set

The Full Analysis Set (FAS) will consist of all enrolled patients in the SC arm who have signed the ICF and who have at least one valid non-safety assessment after enrollment as well as all patients randomized to the CIG or IQOS arm who have signed the ICF, have at least one valid non-safety assessment after randomization and have at least one post-randomization product (IQOS or CIG) use experience. The FAS will be analyzed by enrolled arm (randomization arm for CIG or IQOS, or SC arm) and by product use category (see section 5.7).

Confidentiality Statement

Data and information contained in this document are considered to constitute trade secrets and confidential commercial information, and the legal protections provided to such trade secrets and confidential information are hereby claimed under the provisions of applicable law. No part of this document may be publicly disclosed without the written consent of Philip Morris Products S.A

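### SAP 9.5.1.1 fits a growth slope per patient with no minimum number of scans and no rule for a slope that cannot be estimated, so a one-scan patient may enter the primary summary as 0 mm/year

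*SAP*

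**What the plan says.** SAP 3.1 names the primary endpoint as "AAA annual growth rate (calculated by annualizing the slope of the linear regression over the available diameter measurements" and limits the data in its lead-in: "Endpoints (to be assessed using all available diameter measurements from V3 to V8".

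SAP 9.5.1.1 describes the fit in two ways. The prose speaks of a "linear regression fit to the maximum minor-axis AAA diameter values over the time by randomization arm". The sample code fits each patient separately, "by subject; model AAA diameter = Study day", and then keeps the whole coefficient table: "ods output ParameterEstimates = out1; run". The planned result is stated as "Descriptive statistics for the annualized mean growth rates of AAA will be presented", in the Full Analysis Set (FAS), by study arm and by product use category.

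Other sections decide whether a patient can arrive there with one scan:

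- **Entry to the FAS (SAP 8.1).** Randomized patients must "have at least one valid non-safety assessment after randomization and have at least one post-randomization product" use. Smoking-cessation patients need one non-safety assessment after enrolment. No number of CT scans is required.
- **Baseline scan.** V1 is not among the target visits in SAP 9.5.1.1. SAP 9.5.1.2 does list V1 for the diameter summary, so the omission looks deliberate.
- **Unscheduled scans (SAP 9.1.6).** They go into listings, not tables.
- **Exit.** Protocol 5.2.1 requires discontinuation when, among other reasons, "Patient has to undergo open surgical AAA treatment or AAA endovascular repair". Table 7 in protocol 9.4 lists no CT scan at early termination, although the end of protocol 9.3 extends the pre-discharge V8 procedures to early termination.
- **Missing data.** SAP 9.1.5 gives rules for exposure biomarkers and product use only. SAP 9.1.3 asks for the number with a value and the number and percentage missing.

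**The concern.** A patient who leaves between V3 and V4 can be in the FAS with exactly one usable diameter. One diameter carries no information about growth, yet nothing in the plan says that this patient has no growth rate. If the code is followed literally, the software may supply a number in place of a missing value, and that number is zero.

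A zero would enter the mean, SD, quartiles and 95% CI of the primary endpoint. It would not appear in the missing count, so the summary table would give no sign of it. The arms are small: protocol 4.4 reports 32 patients enrolled, across three arms, when the decision to stop recruitment was explained. A single value therefore has visible weight. If the problem were noticed only after database lock, its handling would be chosen when the study statisticians are no longer blinded to the primary endpoint (SAP 4.3.2.2).

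**Working it through.** The documents state no expected growth rate, SD, dropout rate or arm size, so there is no planned figure to reproduce. The check has two parts.

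**1. What one scan gives.** Take one record at study day 183 with a diameter of 42 mm (example values). The model is diameter = a + b × day.

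- The cross-product matrix of intercept and day is [1, 183; 183, 33,489]. Its determinant is 33,489 − 183² = 0, so a and b are not separately identified.
- Taking the intercept first leaves 33,489 − 183²/1 = 0 for the day term. The usual PROC REG convention for a redundant term sets its coefficient to 0 with 0 degrees of freedom. Coding that convention outside SAS returned intercept 42, slope 0, slope degrees of freedom 0.
- The zero is a convention, not an estimate. The minimum-norm (Moore-Penrose) solution for the same record gives a slope of 83.8 mm/year.
- As a control, the same routine gave 2.00 mm/year for two scans (42 and 43 mm, 183 days apart) and 2.00 mm/year for six scans on an exact 2 mm/year line. Only the one-scan case misbehaves.

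SAS itself was not run. The calculation shows what follows from the convention; it does not prove what the production program will print.

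**2. Effect on an arm mean.** If n patients would average m, and k of them (with no systematic difference from the rest) are recorded as 0, the reported mean is m × (n − k)/n. The relative shift is k/n toward zero.

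Inputs, all assumed: n = 11, from 32/3 = 10.7 rounded up; m = 2 mm/year; k = 1 or 2.

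- k = 1: 2 × 10/11 = 1.82, a shift of −0.18 mm/year (9%).
- k = 2: 2 × 9/11 = 1.64, a shift of −0.36 mm/year (18%).

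Range for n = 8 to 16 and m = 1 to 4 mm/year:

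| k | relative shift | shift in mm/year |
|---|---|---|
| 1 | 6.25% to 12.5% | 0.06 to 0.50 |
| 2 | 12.5% to 25% | 0.13 to 1.00 |

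For scale, protocol 2.1 cites a difference of about 0.4 mm/year between smokers and former smokers.

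Setting the one-scan slope to missing changes the picture as follows. With 10 patients, nine averaging 2.0 mm/year and one with a single scan, the table shows mean 1.80, n = 10, none missing if the zero is kept. It shows mean 2.00, n = 9, one missing if the slope is treated as not estimable.

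**The case against.** Several points on the other side are sound.

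- **The block is sample code.** It uses placeholder names and contains no V3 to V8 selection, no annualisation and no summary step. A programmer could filter before or after it, and the planned listing of REG output would show rows with 0 degrees of freedom. This stands. A reader might infer that the plan as written will certainly report zeros; the documents do not show that. They show that nothing tells the programmer to do otherwise.
- **The adjacent prose describes another fit.** One pooled regression per arm would create no per-patient zeros. The request for descriptive statistics on growth rates points to one value per patient, but the conflict is real and has to be settled first.
- **The size is assumed.** Arm sizes, mean growth and the number of one-scan patients are not in the documents. Only IQOS and cigarettes are allocated 1:1, so equal thirds is a convenience. Two one-scan patients out of 11 is 18% of an arm, and zeros in both arms would partly cancel. The 0.4 mm/year contrast is not IQOS versus cigarettes.
- **The direction is toward zero.** It is downward only when mean growth is positive, which the entry requirement for earlier growth makes likely but does not guarantee.
- **Repair soon after V3.** One might infer that fast growers sent for repair would be recorded as not growing. This is possible, but its frequency is unknown. Entry diameters are capped at 49 mm for men and 44 mm for women, while the indicators cited in protocol 2.1 are 55 mm and 50 mm, or 5 mm in six months. Whether such a patient would have an exit CT is also unclear, because protocol 9.3 and Table 7 do not agree.
- **The study is descriptive.** No hypothesis is tested, and medians and quartiles are reported beside the mean.

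These points limit the claim. They do not supply the missing rule.

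**Conclusion.** The gap is established from the documents: slopes per patient in the code, V3 to V8 scans only, no minimum number of scans, no rule for a slope that cannot be estimated, and FAS entry open to a patient with one such scan. The consequence is conditional. It needs at least one patient with a single V3 to V8 scan, the usual PROC REG behaviour (to be confirmed in SAS), and a programmer who keeps the row with 0 degrees of freedom. If all three hold, the arm mean moves toward zero by k/n and the summary does not count the patient as missing. Under the assumed 11 patients and 2 mm/year, that is 0.18 mm/year for one patient and 0.36 for two.

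This should be fixed before database lock. It would be too strong to say that the primary result is wrong as planned or that the analysis cannot proceed: the flaw is conditional, the study is descriptive, and the remedy is small.

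**What to change.** In SAP 9.5.1.1:

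1. State that the growth rate is fitted for each patient and then summarised by arm, and bring the prose into line with the code.
2. State that the growth rate is set to missing for a patient with fewer than two V3 to V8 diameters on different dates. This also covers patients with no V3 to V8 scan.
3. State that coefficient rows with 0 degrees of freedom are dropped before the summary.
4. Count these patients as missing, by arm, under SAP 9.1.3.

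In the program, count non-missing diameters on distinct dates and run the regression only where there are at least two. A short SAS test with a one-record patient would confirm the behaviour. Separately, reconcile the end of protocol 9.3 with Table 7 on which procedures apply at early termination, since this affects how many patients have a single scan.

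The cost is a few sentences and one data step. The only downside is that the n in the growth-rate table may be slightly smaller than the FAS n, which the missing count then explains.
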